3.5. Discontinuation Criteria

The medical monitor should be consulted prior to subject discontinuation when medically feasible. Study medication must be discontinued in the following instances:

- Intercurrent illness that would, in the judgment of the investigator, affect assessments of clinical status to a significant degree. Following resolution of intercurrent illness, the subject may resume study dosing at the discretion of the investigator
- Unacceptable toxicity (as defined in Section 7.5 of the protocol) or toxicity that, in the judgment of the investigator, compromises the ability to continue study-specific procedures or is considered to not be in the subject's best interest
- Pregnancy of female subject or female partner of male subject
- Efficacy failure as defined in Section 3.4
- Significant protocol violation including non-compliance with study assessments
- Subject or parent/legal guardian request to discontinue for any reason; it is important to determine whether the withdrawal of consent is primarily due to an AE, lack of efficacy, or other reason
- Discontinuation of the study at the request of Gilead, regulatory agency, or an Independent Ethics Committee (IEC)

Subjects who meet any of the following criteria must stop treatment with SOF/VEL/VOX FDC:

- Elevation of ALT and/or AST above the upper limit of normal and $> 5x$ Day 1 or nadir, confirmed by immediate repeat testing
- Elevation of ALT $> 3x$ Day 1 and total bilirubin $> 2x$ ULN, confirmed by immediate repeat testing
- Any Grade 3 or greater rash associated with constitutional symptoms (see Appendix 3)
- Any Grade 4 adverse event assessed as related to administration of SOF/VEL/VOX FDC (see Appendix 3)

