7.2.2. Assessment of Severity

The severity grading of AEs will be assessed as Grade 1, 2, 3, or 4 using the GSI Grading Scale for Severity of Adverse Events and Laboratory Abnormalities ([Appendix 3](#)). For AEs associated with laboratory abnormalities, the event should be graded on the basis of the clinical severity in the context of the underlying conditions; this may or may not be in agreement with the grading of the laboratory abnormality.

7.3. Investigator Requirements and Instructions for Reporting Adverse Events and Serious Adverse Events to Gilead

Requirements for collection prior to study drug initiation:

After informed consent, but prior to initiation of study medication, the following types of events should be reported on the eCRF: all SAEs and adverse events related to protocol mandated procedures.

Adverse Events

Following initiation of study medication, collect all AEs, regardless of cause or relationship, until 30 days after last administration of study IMP and report to the eCRF database as instructed.

All AEs should be followed up until resolution or until the adverse event is stable, if possible. Gilead Sciences may request that certain AEs be followed beyond the protocol defined follow up period.

Serious Adverse Events

All SAEs, regardless of cause or relationship, that occurs after the subject first consents to participate in the study (ie, signing the informed consent) and throughout the duration of the study, including the protocol-required posttreatment follow-up period, must be reported to the eCRF database and Gilead Pharmacovigilance and Epidemiology (PVE) as instructed. This also includes any SAEs resulting from protocol associated procedures performed after informed consent is signed.

Any SAEs and deaths that occur after the posttreatment follow-up visit but within 30 days of the last dose of study IMP, regardless of causality, should also be reported.

Investigators are not obligated to actively seek SAEs after the protocol defined follow up period; however, if the investigator learns of any SAEs that occur after study participation has concluded and the event is deemed relevant to the use of IMP, he/she should promptly document and report the event to Gilead PVE.

- All AEs and SAEs will be recorded in the eCRF database within the timelines outlined in the eCRF completion guideline.

Electronic Serious Adverse Event (eSAE) Reporting Process

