ALT (SGPT)	1.25 to 2.50 × ULN	> 2.50 to 5.00 × ULN	> 5.00 to 10.00 × ULN	> 10.00 × ULN
GGT	1.25 to 2.50 × ULN	> 2.50 to 5.00 × ULN	> 5.00 to 10.00 × ULN	> 10.00 × ULN
Alkaline Phosphatase	1.25 to 2.50 × ULN	> 2.50 to 5.00 × ULN	> 5.00 to 10.00 × ULN	> 10.00 × ULN
Total Amylase	> 1.0 to 1.5 × ULN	> 1.5 to 2.0 × ULN	> 2.0 to 5.0 × ULN	> 5.0 × ULN
Pancreatic Amylase	> 1.0 to 1.5 × ULN	> 1.5 to 2.0 × ULN	> 2.0 to 5.0 × ULN	> 5.0 × ULN
Lipase	> 1.0 to 1.5 × ULN	> 1.5 to 3.0 × ULN	> 3.0 to 5.0 × ULN	> 5.0 × ULN
Albumin	-	2.0 to < LLN g/dL	< 2.0 g/dL	NA
Pediatrics <16 years		20 to < LLN g/L	< 20 g/L	
≥ 16 years	3.0 g/dL to < LLN 30 g/L to < LLN	2.0 to < 3.0 g/dL 20 to < 30 g/L	< 2.0 g/dL < 20 g/L	NA

URINALYSIS				
	Grade 1	Grade 2	Grade 3	Grade 4
Hematuria (Dipstick)	1+	2+	3-4+	NA
Hematuria (Quantitative) See Note below				
Females	>ULN - 10 RBC/HPF	> 10-75 RBC/HPF	> 75 RBC/HPF	NA
Males	6-10 RBC/HPF	> 10-75 RBC/HPF	> 75 RBC/HPF	NA
Proteinuria (Dipstick)	1+	2-3+	4+	NA
Proteinuria, 24 Hour Collection				
Adult and Pediatric ≥ 10 Years	200 to 999 mg/24 h	>999 to 1999 mg/24 h	>1999 to 3500 mg/24 h	> 3500 mg/24 h
Pediatric > 3 Mo to < 10 Years	201 to 499 mg/m ² /24 h	>499 to 799 mg/m ² /24 h	>799 to 1000 mg/m ² /24 h	> 1000 mg/ m ² /24 h
Glycosuria (Dipstick)	1+	2-3+	4+	NA

Notes:

- Toxicity grades for Quantitative and Dipstick Hematuria will be assigned by Covance Laboratory, however for other laboratories, toxicity grades will only be assigned to Dipstick Hematuria.
- With the exception of lipid tests, any graded laboratory test with a result that is between the LLN and ULN should be assigned Grade 0.
- If the severity of a clinical AE could fall under either one of two grades (eg, the severity of an AE could be either Grade 2 or Grade 3), select the higher of the two grades for the AE.

CARDIOVASCULAR				
	Grade 1	Grade 2	Grade 3	Grade 4
Cardiac Arrhythmia (general) (By ECG or physical exam)	Asymptomatic AND No intervention indicated	Asymptomatic AND Non-urgent medical intervention indicated	Symptomatic, non-life-threatening AND Non-urgent medical intervention indicated	Life-threatening arrhythmia OR Urgent intervention indicated
Cardiac-ischemia/Infarction	NA	NA	Symptomatic ischemia (stable angina) OR Testing consistent with ischemia	Unstable angina OR Acute myocardial infarction

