Hemorrhage (significant acute blood loss)	NA	Symptomatic AND No transfusion indicated	Symptomatic AND Transfusion of ≤ 2 units packed RBCs (for children ≤ 10 cc/kg) indicated	Life-threatening hypotension OR Transfusion of > 2 units packed RBCs indicated (for children ≤ 10 cc/kg) indicated
Hypertension (with repeat testing at same visit)	140–159 mmHg systolic OR 90–99 mmHg diastolic	> 159–179 mmHg systolic OR > 99–109 mmHg diastolic	> 179 mmHg systolic OR > 109 mmHg diastolic	Life-threatening consequences (eg, malignant hypertension) OR Hospitalization (other than ER visit) indicated
Pediatric ≤ 17 Years (with repeat testing at same visit)	NA	91st–94th percentile adjusted for age, height, and gender (systolic and/or diastolic)	≥ 95th percentile adjusted for age, height, and gender (systolic and/or diastolic)	Life-threatening consequences (eg, malignant hypertension) OR Hospitalization indicated (other than emergency room visit)
Hypotension	NA	Symptomatic, corrected with oral fluid replacement	Symptomatic, IV fluids indicated	Shock requiring use of vasopressors or mechanical assistance to maintain blood pressure
Pericardial Effusion	Asymptomatic, small effusion requiring no intervention	Asymptomatic, moderate or larger effusion requiring no intervention	Effusion with non-life-threatening physiologic consequences OR Effusion with nonurgent intervention indicated	Life-threatening consequences (eg, tamponade) OR Urgent intervention indicated

CARDIOVASCULAR				
	Grade 1	Grade 2	Grade 3	Grade 4
Prolonged PR Interval	PR interval 0.21 to 0.25 sec	PR interval > 0.25 sec	Type II 2nd degree AV block OR Ventricular pause > 3.0 sec	Complete AV block
Pediatric ≤ 16 Years	1st degree AV block (PR > normal for age and rate)	Type I 2nd degree AV block	Type II 2nd degree AV block	Complete AV block
Prolonged QTc	Asymptomatic, QTc interval 0.45 to 0.47 sec OR Increase interval < 0.03 sec above baseline	Asymptomatic, QTc interval 0.48 to 0.49 sec OR Increase in interval 0.03 to 0.05 sec above baseline	Asymptomatic, QTc interval ≥ 0.50 sec OR Increase in interval ≥ 0.06 sec above baseline	Life-threatening consequences, eg, Torsade de pointes or other associated serious ventricular dysrhythmia
Pediatric ≤ 16 Years	Asymptomatic, QTc interval 0.450 to 0.464 sec	Asymptomatic, QTc interval 0.465 to 0.479 sec	Asymptomatic, QTc interval ≥ 0.480 sec	Life-threatening consequences, eg, Torsade de pointes or other associated serious ventricular dysrhythmia

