7.1.2. Adverse Event Severity

Adverse events are graded by the investigator as Grade 1, 2, 3, or 4 according to toxicity criteria specified in the protocol. The severity grade of events for which the investigator did not record severity will be categorized as “missing” for tabular summaries and data listings and the most severe will be considered (for sorting purpose only) in data presentation.

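### Hemorrhage grading in Appendix 3: the child transfusion limit is ≤ 10 cc/kg in both Grade 3 and Grade 4, so the smaller transfusion grades as 4 and the larger has no volume grade

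*Protocol*

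**What the plan says.** Three cells of the Hemorrhage row (Protocol Appendix 3, Cardiovascular) set the grades:

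- Grade 2: "Symptomatic AND No transfusion indicated".
- Grade 3: symptomatic, and "Transfusion of ≤ 2 units packed RBCs (for children ≤ 10 cc/kg) indicated".
- Grade 4: life-threatening hypotension, or "Transfusion of > 2 units packed RBCs indicated (for children ≤ 10 cc/kg) indicated".

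The notes in the same appendix deal with a clinical event that could take either of two grades. The instruction is to "select the higher of the two grades for the AE".

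The scale governs grading in this trial. Under Protocol 7.2.2, adverse events "will be assessed as Grade 1, 2, 3, or 4 using the GSI Grading Scale". SAP 7.1.2 takes over the investigator's grade, assigned "according to toxicity criteria specified in the protocol". Protocol 3.5 lists among the events after which treatment must stop: "Any Grade 4 adverse event assessed as related to administration of SOF/VEL/VOX FDC".

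**The concern.** Two adjacent severity grades cannot share one volume limit. The adult pair in this row is complementary and the child pair is identical, which points to a slip for > 10 cc/kg in the Grade 4 cell. That cell also repeats a word, as if it had been edited carelessly.

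Read literally, the child scale runs backwards. The smaller transfusion is pushed up to Grade 4, and the larger one has no volume criterion at all. Because a related Grade 4 event triggers a mandatory stop, the row can end treatment for the lesser bleed and stay silent on the greater one. The ungraded event also leaves the investigator to invent a grade, and that grade decides whether the event enters the AE tables for Grade 3 or above (SAP 7.1.6).

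A smaller matter is that the row does not say who counts as a child. The neighbouring Hypertension row does give an age, with a pediatric line for subjects aged 17 years or younger. The protocol enrols ages 3 to < 18, so the child limit is not a side case here.

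**Working it through.** This is a check of logic, with one illustration in numbers.

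**Grades for a subject graded by cc/kg.** Let v be the transfusion volume indicated for a symptomatic bleed without life-threatening hypotension.

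| v | Grade 2 (no transfusion) | Grade 3 (v ≤ 10) | Grade 4 as printed (v ≤ 10) | Result as printed | Result if Grade 4 is v > 10 |
|---|---|---|---|---|---|
| 5 cc/kg | no | yes | yes | Grade 4, by the tie-break note | Grade 3 |
| 15 cc/kg | no | no | no | no matching cell | Grade 4 |

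The corrected limit removes both the overlap and the gap, and reproduces the adult pattern of ≤ 2 versus > 2 units.

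**Illustration at 35 kg.** The documents give no volume for a unit of red cells, so I assume 250 to 350 mL. The weight is illustrative and is not an eligibility limit.

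- 10 cc/kg × 35 kg = 350 mL.
- One unit: 250/35 = 7.1 to 350/35 = 10.0 cc/kg.
- Two units: 500/35 = 14.3 to 700/35 = 20.0 cc/kg.

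| Transfusion at 35 kg | By units | By cc/kg as printed | By cc/kg corrected |
|---|---|---|---|
| One unit | Grade 3 | Grade 4 | Grade 3 |
| Two units | Grade 3 | no volume grade | Grade 4 |

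**Does the choice of rule matter for adolescents once the sign is corrected?** Two units equal 10 cc/kg at 500/10 = 50 kg (250 mL per unit) to 700/10 = 70 kg (350 mL per unit). Below that weight, two units are Grade 3 by units and Grade 4 by the corrected cc/kg limit. At 60 kg, two units are 500/60 = 8.3 to 700/60 = 11.7 cc/kg, so the assumed unit volume decides. Many subjects aged 12 to < 18 could plausibly weigh less than 50 to 70 kg, although the documents give no weight distribution.

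**The case against.** The case for leaving this alone has several parts.

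- **It may reach no analysed subject.** SAP 2.2 records a waiver for those under 12, and the analysis sets are adolescent-only. Protocol 1.4 distinguishes adolescents of 12 to < 18 from children below 12. If that usage carries into Appendix 3, adolescents are graded by units and the printed limits work. This stands as a possibility but is not settled: Appendix 3 does not define the term, and Protocol 1.1 speaks of children up to 15.
- **The event is remote.** Protocol 4.3 excludes prior variceal hemorrhage and other decompensation, INR > 1.2 × ULN and platelets < 50,000/mm³. SAP 3.2 says only DAA-naive subjects without cirrhosis were enrolled, on 8 weeks of treatment. The bleed must also be judged drug-related before the mandatory stop applies. All of this stands.
- **There is a backstop.** Protocol 3.5 also has treatment stopped for toxicity on the investigator's judgment, so a related bleed needing more than 10 cc/kg would probably end treatment anyway. For the smaller volume the error is on the cautious side. This too stands.
- **Reporting hardly moves.** SAP 7.1.6 tabulates Grade 2 or above and Grade 3 or above, with no separate Grade 4 table. Moving an event between Grades 3 and 4 therefore changes no listed count. That is right for 10 cc/kg or less. It does not help above 10 cc/kg, where no cell matches.
- **The sign may have been misread from the PDF.** This cannot be fully excluded, but the adult > in the same cell came through correctly, so it is unlikely.

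These points limit the importance of the error. None of them makes the printed limit right.

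**Conclusion.** The concern holds. As printed, the Grade 4 child limit is wrong, and no other text in the protocol or SAP corrects it. For subjects graded by cc/kg, the row inverts the severity order and leaves volumes above 10 cc/kg without a volume grade.

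The consequence is minor. It depends on a rare transfusion-requiring bleed and on cc/kg being the rule applied; the mandatory stop further depends on the bleed being judged drug-related. Neither the primary PK endpoint nor SVR12 is affected. The numerical illustration rests on an assumed unit volume of 250 to 350 mL. The missing age range is a secondary point that would not justify a change by itself.

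**What to change.** Change the child limit in the Grade 4 Hemorrhage cell to > 10 cc/kg. While editing the row, state the age range to which cc/kg applies, in the style of the Hypertension row, so that sites know which rule grades subjects aged 12 to < 18.

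The cost is one cell and one age label in the next amendment, or a short grading clarification to sites if no amendment is planned. No new data are needed. Since the SAP describes enrolment in the past tense, few or no further events may be graded in this trial. The remaining step would then be to check whether any recorded hemorrhage needed a transfusion and, if so, which rule was used.

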Appendix 4. Tanner Stages*

1. Pubic hair (male and female)	
Tanner I	no pubic hair at all (prepubertal Dominic state)
Tanner II	small amount of long, downy hair with slight pigmentation at the base of the penis and scrotum (males) or on the labia majora (females)
Tanner III	hair becomes more coarse and curly, and begins to extend laterally
Tanner IV	adult-like hair quality, extending across pubis but sparing medial thighs
Tanner V	hair extends to medial surface of the thighs
2. Genitals (male) (One standard deviation around mean age)	
Tanner I	Testes, scrotum, and penis about same size and proportion as in early childhood
Tanner II	Enlargement of scrotum and testes; skin of scrotum reddens and changes in texture; little or no enlargement of penis (10.5-12.5)
Tanner III	Enlargement of penis, first mainly in length; further growth of testes and scrotum (11.5-14)
Tanner IV	Increased size of penis with growth in breadth and development of glans; further enlargement of testes and scrotum and increased darkening of scrotal skin (13.5-15)
Tanner V	Genitalia adult in size and shape
3. Breasts (female)	
Tanner I	no glandular tissue: areola follows the skin contours of the chest
Tanner II	breast bud forms, with small area of surrounding glandular tissue; areola begins to widen
Tanner III	breast begins to become more elevated, and extends beyond the borders of the areola, which continues to widen but remains in contour with surrounding breast
Tanner IV	increased breast size and elevation; areola and papilla form a secondary mound projecting from the contour of the surrounding breast
Tanner V	breast reaches final adult size; areola returns to contour of the surrounding breast, with a projecting central papilla.

* Chart referenced from Marshall WA, Tanner JM, variations in the pattern of pubertal changes in boys and girls {[Marshall 1969](#), [Marshall 1970](#)}

Appendix 5. Pregnancy Precautions, Definition for Female of Childbearing Potential, and Contraceptive Requirements

1) Definitions

a. Definition of Childbearing Potential

For the purposes of this study, a female born subject is considered of childbearing potential following the initiation of puberty (Tanner stage 2) until becoming postmenopausal, unless permanently sterile or with medically documented ovarian failure.

Women of any age with amenorrhea of ≥ 12 months may be considered postmenopausal if their follicle stimulating hormone (FSH) level is in the postmenopausal range and they are not using hormonal contraception or hormonal replacement therapy.

Permanent sterilization includes hysterectomy, bilateral oophorectomy, or bilateral salpingectomy in a female subject of any age.

b. Definition of Male Fertility

For the purposes of this study, a male born subject is considered of fertile after the initiation of puberty unless permanently sterile by bilateral orchidectomy or medical documentation.

2) Study Drug Effects on Pregnancy and Hormonal Contraception

Data on the effects of SOF/VEL/VOX FDC on pregnant women is not available.

From nonclinical studies, there is no evidence that SOF, VEL, or VOX is genotoxic. Relevant nonclinical reproductive studies have demonstrated no adverse effect on fertility or embryo-fetal development for SOF, VEL, and VOX as individual agents.

Data from clinical pharmacokinetic interaction studies of SOF/VEL/VOX FDC have demonstrated that there is no reduction in the clinical efficacy of hormonal contraception.

3) Contraception Requirements for Female Subjects

The inclusion of female subjects of childbearing potential requires using at least an acceptable effective contraceptive measure. They must have a negative serum pregnancy test at Screening and a negative pregnancy test on the Day 1 visit prior to enrollment. Pregnancy tests will be performed every 4 weeks during the dosing period and at the posttreatment Week 4 visit. They must also agree to one of the following from Screening until 30 days of the last dose of SOF/VEL/VOX FDC.

- Complete abstinence from intercourse of reproductive potential. Abstinence is an acceptable method of contraception only when it is in line with the subject's preferred and usual lifestyle.

Or

- Consistent and correct use of 1 of the following methods of birth control listed below.
 - Intrauterine device (IUD)
 - Intrauterine hormone-releasing system (IUS)
 - Tubal sterilization
 - Vasectomy in the male partner
 - Barrier methods (one female barrier and one male barrier must be used in combination)
 - Female barriers: Diaphragm with spermicide or Cervical cap with spermicide
 - Male barriers: Male condom (with or without spermicide)
 - Hormonal methods
 - Oral contraceptives (progesterone only)
 - Injectable progesterone
 - Implants of levonorgestrel or etonorgestrel

Female subjects must also refrain from egg donation and in vitro fertilization during treatment and until at least 30 days after the last dose of SOF/VEL/VOX FDC.

4) Contraception Requirements for Male Subjects

During the study, male subjects with female partners of childbearing potential should use condoms until 30 days after the last dose of SOF/VEL/VOX FDC treatment when engaging in intercourse of reproductive potential. If their female partner is of childbearing potential (as defined above), their female partner must use 1 of the methods of birth control listed above from the date of Screening until 30 days after the last dose of SOF/VEL/VOX FDC.

Male subjects must agree to refrain from sperm donation until 30 days after the last dose of SOF/VEL/VOX FDC.

5) Unacceptable Birth Control Methods

Birth control methods that are unacceptable include periodic abstinence (eg, calendar, ovulation, symptothermal, and post-ovulation methods), withdrawal (coitus interruptus), spermicides only, and lactational amenorrhea method (LAM). Female condom and male condom should not be used together.

6) Procedures to be Followed in the Event of Pregnancy

Subjects will be instructed to notify the investigator if they become pregnant at any time during the study, or if they become pregnant within 30 days of last study drug dose. Subjects who become pregnant or who suspect that they are pregnant during the study must report the information to the investigator and discontinue study drug immediately. Subjects whose partner has become pregnant or suspects she is pregnant during the study must report the information to the investigator. Instructions for reporting pregnancy, partner pregnancy, and pregnancy outcome are outlined in Section [7.6.2.1](#).

RNA	ribonucleic acid

SAE	serious adverse event
SAP	statistical analysis plan
SI (units)	International system of units
SOC	system organ class
SOF	sofosbuvir
SVR	sustained virologic response
SVRx	sustained virologic response x weeks after stopping study drug
TEAE	treatment-emergent adverse events
TFLs	tables, figures, and listings
TND	target not detected
ULN	upper limit of normal
VEL	velpatasvir
VF	virologic failure
VOX	voxilaprevir
WBC	white blood cell
WHO	World Health Organization

PHARMACOKINETIC ABBREVIATIONS AND DEFINITIONS

AUC	area under the plasma/serum concentration versus time curve
AUC _{tau}	area under the plasma/serum concentration versus time curve over the dosing interval
C _{max}	maximum observed plasma/serum concentration of drug
C _{tau}	observed drug concentration at the end of the dosing interval

1. INTRODUCTION

This statistical analysis plan (SAP) describes the statistical analysis methods and data presentations to be used in tables, figures, and listings (TFLs) for Study GS-US-367-1175. This SAP is based on study Protocol Amendment 1 dated 27 March 2019 and electronic case report form (eCRF). Any changes made after the finalization of the SAP will be documented in the clinical study report (CSR).

